### 9.3 Response Criteria

#### 9.3.1 Evaluation of target lesions

Complete Response (CR): Disappearance of all target lesions

Partial Response (PR): At least a 30% decrease in the sum of the longest diameter (LD) of target lesions, taking as reference the baseline sum LD

Progressive Disease (PD): At least a 20% increase in the sum of the LD of target lesions, taking as reference the smallest sum LD recorded since the treatment started or the appearance of one or more new lesions

Stable Disease (SD): Neither sufficient shrinkage to qualify for PR nor sufficient increase to qualify for PD, taking as reference the smallest sum LD since the treatment started

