### **3. PATIENT SELECTION**

#### **3.1 Inclusion Criteria**

- 3.1.1 Patients must have histologically or cytologically confirmed squamous cell carcinoma of the skin. Patients who present with "squamous cell carcinoma of unknown primary lesions" at the time of diagnosis will be eligible if patients have a plausible primary skin site removed in the past. Similarly, patients with neck, parotid, or facial lymph nodes positive for squamous cell carcinoma with no identifiable mucosal primary would also be eligible.

- 3.1.2 Patients must have measurable disease, defined by RECIST v1.1 as at least one lesion that can be accurately measured in at least one dimension of  $\geq 10$  mm by CT, MRI, or calipers. See section 9.2 for the evaluation of measurable disease.
- 3.1.3 There is no limitation to prior treatments with local, regional, topical or systemic agents, except for prior systemic treatment with 5-fluorouracil or prodrugs thereof. Prior topical treatment with 5-fluorouracil is permitted. Patients who are on chronic daily doses of prednisone of greater than 10 mg are excluded. There is no restriction on timing of last treatments as long as patients have recovered from all expected toxicities and at least 21 days have passed since last administration.
- 3.1.4 Age  $\geq 18$  years. Because no dosing or adverse event data are currently available on the use of 5-FU/Capecitabine or IFN alpha-2b in patients  $<18$  years of age, children are excluded from this study.
- 3.1.5 Life expectancy of greater than 3 months.
- 3.1.6 ECOG performance status  $\leq 2$  (Karnofsky  $\geq 60\%$ ; see Appendix A).
- 3.1.7 Patients must have normal organ and marrow function as defined below:
 

Absolute neutrophil count	$\geq 1,500/\text{mcL}$
Platelets	$\geq 75,000/\text{mcL}$
Total Bilirubin	$< \text{ULN}$ or up to 2x ULN if patient has clinically documented Gilbert's syndrome (elevated unconjugated bilirubin from decreased UGT1A1 activity)
AST(SGOT)/ALT(SGPT)	$\leq 2.5x$ institutional upper limit of normal or up to 5x ULN if known to be caused by liver metastasis
Creatinine Clearance	$\geq 50 \text{ mL/min}$ by either Cockcroft-Gault formula or 24 hr urine collection analysis.

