#### 9.1 Definitions

Response and progression will be evaluated in this study using the new international criteria proposed by the Response Evaluation Criteria in Solid Tumors (RECIST) v1.1 Committee [JNCI 92(3):205-216, 2000]. Changes in only the largest diameter (unidimensional measurement) of the tumor lesions are used in the RECIST criteria. Note: Lesions are either measurable or non-measurable using the criteria provided below. The term “evaluable” in reference to measurability will not be used because it does not provide additional meaning or accuracy.

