##### 9.1.1 Measurable disease

Measurable lesions are defined as those that can be accurately measured in at least one dimension (longest diameter to be recorded) as  $\geq 10$  mm with conventional techniques (CT, MRI, x-ray). All tumor measurements must be recorded in millimeters (or decimal fractions of centimeters).

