## 9.2 Guidelines for Evaluation of Measurable Disease

All measurements should be taken and recorded in metric notation using a ruler or calipers. All baseline evaluations should be performed as closely as possible to the beginning of treatment and never more than 4 weeks before the beginning of the treatment.

The same method of assessment and the same technique should be used to characterize each identified and reported lesion at baseline and during follow-up. Imaging-based evaluation is preferred to evaluation by clinical examination when both methods have been used to assess the antitumor effect of a treatment.

**Clinical lesions.** Clinical lesions will only be considered measurable when they are superficial (e.g., skin nodules and palpable lymph nodes). In the case of skin lesions, documentation by calipers or color photography (including a ruler to estimate the size of the lesion) is recommended.

**Conventional CT and MRI.** These techniques should be performed with cuts of 10 mm or less in slice thickness contiguously. Spiral CT should be performed using a 5 mm contiguous reconstruction algorithm. This applies to tumors of the chest, abdomen, and pelvis. Head and neck tumors and those of extremities usually require

specific protocols.

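### Section 9 names RECIST v1.1 but mixes criteria, and its progression rule has no absolute minimum, so for small tumour sums a change within plausible measurement error counts as progression

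*Combined protocol and SAP*

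**What the plan says.** **Version.** Section 3.1.2 reads "Patients must have measurable disease, defined by RECIST v1.1 as at least one lesion that can be accurately measured in at least one dimension", with a limit of 10 mm or more by CT, MRI or calipers. Section 9.1 attributes the criteria to the "Response Evaluation Criteria in Solid Tumors (RECIST) v1.1 Committee [JNCI 92(3):205-216, 2000", so a v1.1 label carries a reference from 2000.

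**Measurability.** Under 9.1.1 a lesion is measurable if it "can be accurately measured in at least one dimension (longest diameter to be recorded) as" 10 mm or more by conventional techniques, listed as CT, MRI and x-ray. Section 9.1.2 puts lesions under 20 mm by conventional techniques, or under 10 mm by spiral CT, in the non-measurable class. Section 9.2 says of conventional CT and MRI: "These techniques should be performed with cuts of 10 mm or less in slice thickness contiguously"; spiral CT uses 5 mm reconstruction.

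**Response and progression.** Section 9.3.1 sets partial response (PR) as "At least a 30% decrease in the sum of the longest diameter (LD) of target lesions, taking as reference the baseline sum LD". Progression (PD) is "At least a 20% increase in the sum of the LD of target lesions, taking as reference the smallest sum LD" since treatment began, or a new lesion. No millimetre minimum appears there or in 9.3.2, 9.3.3, 9.4 or 9.5.

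**What depends on it.** The 9.3.3 table turns target-lesion PD into overall PD, and best response counts what was recorded before progression. Section 9.4.1 requires a repeat assessment 4 weeks after response criteria are first met. Progression ends response duration (9.4.2), is a PFS event (9.5) and is a listed reason for treatment to end (4.4).

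**The concern.** A purely relative rule demands less absolute change as the reference sum gets smaller. The reference is the smallest sum on treatment, so the patients most exposed are those with little disease at entry and those who have responded most deeply. For them the threshold can fall to 2 mm or less, which ordinary variation between two readings can produce.

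Two aspects of the text add to this. Section 9 does not identify one set of criteria, so two assessors could reasonably differ on which lesions are measurable. And 9.3.1 does not say what to record when one reading is both at least 30% below baseline and at least 20% above nadir. Section 9.3.2 provides later confirmation by a review panel or the study chair for progression in non-target lesions only; a borderline target-lesion call has no such check.

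At stake are the PFS estimates, response duration, time on treatment and, in a narrow window, the primary endpoint.

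**Working it through.** **1. The plan's own design figure.** Section 11.2 requires at least 2 responses in 16, then at least 5 in 25, for 10% against 30% with alpha and beta of 0.1. The exact two-stage binomial calculation gives a type I error of 0.0951 and power of 0.9030. The design reproduces and is not in dispute.

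**2. Smallest rise that counts as PD.** Formula: 0.20 × reference sum.

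| Reference sum (mm) | 5 | 7 | 10 | 15 | 20 | 25 | 50 |
|---|---|---|---|---|---|---|---|
| Rise needed (mm) | 1.0 | 1.4 | 2.0 | 3.0 | 4.0 | 5.0 | 10.0 |

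A 10 mm sum is possible at entry under 3.1.2 and 9.1.1, and nadir sums can be smaller.

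**3. False PD per comparison.** Assumptions: one target lesion of unchanged true size L, and two independent readings, each normal with mean L and SD s. The documents give no reading error; s = 1 to 2 mm is assumed. Since y2 − 1.2·y1 has mean −0.2L and variance s²(1 + 1.44), the probability is Φ(−0.2L / (s√2.44)).

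| True size L | s = 1 mm | s = 1.5 mm | s = 2 mm |
|---|---|---|---|
| 10 mm | 10.0% | 19.7% | 26.1% |
| 15 mm | 2.7% | 10.0% | 16.8% |
| 20 mm | 0.5% | 4.4% | 10.0% |

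Example: L = 10, s = 1 gives Φ(−2/1.562) = Φ(−1.28) = 10.0%.

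**4. Repeated looks.** Nine cycles of 21 days are 27 weeks. Re-evaluation every nine weeks (section 9) gives about three comparisons against a running minimum. Simulating 1,000,000 patients under the same assumptions, with baseline included in the minimum, the chance of at least one false PD is 37% to 72% at 10 mm and 3% to 37% at 20 mm.

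**5. Effect of an absolute minimum.** The documents give no value, so 2 to 5 mm is an assumed range. A minimum of f mm matters only for reference sums below f/0.20: 10, 15 or 25 mm for f = 2, 3 or 5. At L = 10 mm, for s = 1 to 2 mm, simulated false PD per comparison becomes 8% to 24% (f = 2), 1.7% to 14% (f = 3) or 0.02% to 3.9% (f = 5).

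**6. Overlap of PR and PD.** Take sums of 30, 10 and 12 mm. The last reading is (30 − 12)/30 = 60% below baseline, so it meets PR. It is (12 − 10)/10 = 20% above nadir, so it meets PD. Both can hold whenever 1.2 × nadir ≤ 0.70 × baseline, that is, when the nadir is at least 1 − 0.70/1.20 = 41.7% below baseline.

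**7. Scale if responses were lost.** The share of true responders lost before confirmation is unknown. For assumed shares of 5%, 10% or 20%, the 30% rate becomes 28.5%, 27% or 24%, and power falls from 0.903 to 0.873, 0.837 or 0.742. Alpha and the sample size do not change.

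**The case against.** The strongest reply is that this is a corner case. The population has unresectable or metastatic disease, and 9.1.3 sums up to 10 target lesions. Two 15 mm lesions already give 30 mm, where even a 5 mm minimum would change nothing. The documents give no distribution of tumour sums, and the reading SDs are assumed. This stands: the percentages describe small single-lesion sums, not a trial-wide rate.

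The 10 mm entry case is also contested. Section 9.1.2 would exclude a lesion under 20 mm measured by conventional technique, so pairing a 10 mm lesion with 10 mm CT cuts takes one side of a conflict. That stands too, but the conflict is itself part of the point, spiral CT and caliper lesions remain, and a nadir sum can reach 10 mm from any baseline.

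A reader might infer more than the documents support:

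- **That a confirmed response can be voided.** It cannot. Under 9.3.3 best response is the best recorded until progression, so a later small rise affects only response duration and PFS.
- **That in the 30, 10, 12 mm case the response certainly fails confirmation.** The 12 mm reading still meets the PR definition. PD taking precedence is a reasonable reading, but 9.3.1 does not state it.
- **That the written rule departs from v1.1 by a known number of millimetres.** The documents do not reproduce the v1.1 text, so any specific value, including 5 mm, must be checked against the source.
- **That the trial's power is reduced by a known amount.** The figures in step 7 rest on assumed shares.

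**Conclusion.** The point holds in limited form. Section 9 names one version of RECIST, cites a 2000 publication for it, contradicts itself on measurable size, and uses a relative progression rule with no absolute minimum. Followed as written, that rule can class measurement noise as progression when the reference sum is small: about 10% to 26% per comparison at 10 mm and 0.5% to 10% at 20 mm, for one unchanged lesion and an assumed reading SD of 1 to 2 mm.

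The consequences are false PFS events, shorter recorded response duration and possible early end of treatment. The primary endpoint is exposed only for a response still awaiting its 4-week repeat assessment, and only if PD prevails over PR. The share of patients affected cannot be estimated from the documents. The two-stage design is sound. The endpoint definition should be amended because the correction is cheap and the response thresholds (2 of 16, 5 of 25) are small enough for single patients to matter.

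**What to change.** By amendment to section 9:

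1. State one governing RECIST version and correct the citation in 9.1.
2. Reconcile 9.1.1 and 9.1.2 (measurable size by technique), the target-lesion limits in 9.1.3 and the definitions in 9.3.1 with that version, and align 3.1.2.
3. Write into the 9.3.1 progression definition whatever absolute-increase condition the governing version requires alongside the 20% rule, with its value taken from the source.
4. State which category is recorded when a reading meets both PR from baseline and PD from nadir, including at the confirmatory assessment.
5. Check that the reference to progression in 4.4 remains consistent with the revised definition.

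The cost is a few lines and one reference, with no change to sample size or decision rule. The downside is small: true progression of very small lesions may be recorded one assessment later.

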## 2. BACKGROUND

### 2.1 Study Disease

While squamous cell carcinoma of the skin is a very common cancer, the true number of cutaneous squamous cell carcinoma (CSCC) cases are difficult to determine, as the national SEER database does not capture non-melanomatous skin cancers (NMSC). However, it has been estimated that there are over 1.5 million cases of NMSC (75% Basal cell carcinoma and 25% Squamous cell carcinoma) diagnosed annually in the US. Besides the known risk factor of UV exposure, an increase in cutaneous squamous cell carcinoma (CSCC) has been noted as a result of rising rates of transplants (BMT and solid organ) and the widespread use of immunosuppressive agents.

The majority of CSCCs are local in origin and are therefore treated with focal therapies including surgery, cryotherapy, topical chemotherapy (imiquimod, topical 5-FU), photodynamic therapy, and radiation therapy. Local control with these therapies typically exceeds 90% and even in patients with recurrent local disease, local control rates remain quite high.

Seventy-five percent of recurrences occur in the first two years and typically recur locally or in regional lymph nodes placing patients at high risk for developing distant metastasis. While metastatic squamous cell cancer of the skin is rare, its' consequences are profound. In one study, 34 of 695 cases of cutaneous squamous cell carcinoma developed metastases for a metastatic rate of approximately 5%. The overall mortality of all patients was 3.4%; however, the mortality rate in the metastatic group exceeded 70%. Similarly, in CSCC patients with distant metastasis, Alam et al. described a 5-yr survival rate of less than 10%.

Thus, while many patients are cured with local therapy, those with unresectable locoregional disease or known sites of distant metastasis have an increased mortality rate. Presently there is no standard accepted treatment for unresectable or metastatic disease.

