### 3.2 Exclusion Criteria

3.2.1 Patients who have had chemotherapy or radiotherapy within 21 days (6 weeks for nitrosoureas or mitomycin C) prior to entering the study or those who have not recovered from adverse events due to agents administered more than 3 weeks earlier.

3.2.2 Patients may not be receiving any other investigational agents.

3.2.3 Patients with known brain metastases should be excluded from this clinical trial because of their poor prognosis and because they often develop progressive neurologic dysfunction that would confound the evaluation of neurologic and other adverse events.

3.2.4 History of allergic reactions attributed to compounds of similar chemical or biologic composition to either 5-FU/Capecitabine or Interferon.

3.2.5 Uncontrolled, ongoing illness including, but not limited to, ongoing or active infection, symptomatic congestive heart failure, unstable angina pectoris, myocardial infarction <30 days, CVA/TIA <30 days, cardiac arrhythmia, or psychiatric illness/social situations that would limit compliance with study requirements.

3.2.6 Pregnant women are excluded from this study because 5-FU/Capecitabine is an anti-metabolite agent with the potential for teratogenic or abortifacient effects. Because there is an unknown but potential risk for adverse events in nursing infants secondary to treatment of the mother with 5-FU/Capecitabine, breastfeeding should be discontinued if the mother is treated with 5-FU/Capecitabine. Pregnancy testing will be completed on all female participants of child-bearing potential by urine analysis.

3.2.8 Any heart or lung transplant patient on immunosuppressive agents. Renal transplant patients are allowed if patient is willing to reduce immunosuppressive agents and understand risk of rejection and possible need to return to dialysis. Patients with CLL or other hematologic malignancies are allowed as long as they meet other criteria listed above.

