## 9. MEASUREMENT OF EFFECT

### Antitumor Effect – Solid Tumors

For the purposes of this study, patients should be re-evaluated for response every nine weeks.

If treatment is held for adverse event recovery thereby extending cycle length, then imaging and tumor measurement intervals may be correspondingly altered so that the patient is imaged every third cycle.

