#### 9.3.2 Evaluation of non-target lesions

Complete Response (CR): Disappearance of all non-target lesions and normalization of tumor marker level

Incomplete Response/  
Stable Disease (SD): Persistence of one or more non-target lesion(s) and/or maintenance of tumor marker level above the normal limits

Progressive Disease (PD): Appearance of one or more new lesions and/or unequivocal progression of existing non-target lesions

Although a clear progression of "non-target" lesions only is exceptional, in such circumstances the opinion of the treating physician should prevail, and the progression status should be confirmed at a later time by the review panel (or study chair).

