#### 9.3.3 Evaluation of best overall response

The best overall response is the best response recorded from the start of the treatment until disease progression/recurrence (taking as reference for progressive disease the smallest measurements recorded since the treatment started). The patient's best response assignment will depend on the achievement of both measurement and confirmation criteria (see section 9.3.1).

Target Lesions	Non-Target Lesions	New Lesions	Overall Response
CR	CR	No	CR

CR	Incomplete response/SD	No	PR
PR	Non-PD	No	PR
SD	Non-PD	No	SD
PD	Any	Yes or No	PD
Any	PD	Yes or No	PD
Any	Any	Yes	PD

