#### **9.4 Confirmatory Measurement/Duration of Response**

##### **9.4.1 Confirmation**

To be assigned a status of PR or CR, changes in tumor measurements must be confirmed by repeat assessments that should be performed 4 weeks after the criteria for response are first met. In the case of SD, follow-up measurements must have met the SD criteria at least once after study entry at a minimum interval of 9 weeks (see section 9.3.3).

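### Sections 9.3.1-9.3.3 count any new lesion as progression, with no exception for an unrelated new primary skin cancer; read literally, this lowers PFS and, to a lesser degree, the response rate

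*Combined protocol and SAP*

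**What the plan says.** **Progression.** For target lesions (Section 9.3.1), progression is a 20% increase in the sum of diameters "or the appearance of one or more new lesions". For non-target lesions (Section 9.3.2) it is "Appearance of one or more new lesions and/or unequivocal progression of existing non-target lesions"; the word about certainty there attaches to existing lesions, not to new ones. In the overall-response table of Section 9.3.3, a new lesion gives PD whatever the target and non-target status.

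**Response.** Section 9.3.3: "The best overall response is the best response recorded from the start of the treatment until disease progression/recurrence". Section 9.4.1 adds that changes qualifying for PR or CR "must be confirmed by repeat assessments that should be performed 4 weeks after the criteria for response are first met". Section 9 sets the assessment interval: "patients should be re-evaluated for response every nine weeks".

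**PFS.** Section 9.5 counts progression or death from the start of treatment. Section 11.4 refers to progression by RECIST.

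**Population.** Section 2.1 names UV exposure as a risk factor and states that "an increase in cutaneous squamous cell carcinoma (CSCC) has been noted as a result of rising rates of transplants" and of wide use of immunosuppressive agents. Section 3.2.8 admits renal-transplant patients who are willing to reduce immunosuppression, and excludes heart and lung transplant patients on immunosuppressive agents. Section 3.1.3 excludes chronic prednisone above 10 mg daily.

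**The concern.** A second, unrelated basal or squamous skin cancer says nothing about whether the index tumour is responding. Under the rule as written it is nevertheless PD. The trial is in a skin cancer, Section 8 schedules a physical examination at the start of each cycle, and Section 9.2 treats superficial skin lesions as assessable by calipers or photography. A new skin primary is therefore likely to be noticed and recorded.

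Two results are exposed:

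- **Response rate (primary).** If the unrelated lesion appears before the confirming assessment, the response window closes and a patient whose index tumour is shrinking counts as a non-responder.
- **PFS (secondary).** Each such lesion in a patient still free of progression is an event, and the exposure lasts as long as PFS is followed.

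Duration of response (Section 9.4.2) is affected in the same way as PFS. Overall survival is not directly affected.

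**Working it through.** **1. Is there an exemption elsewhere?** Two provisions come close, and neither applies.

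- The clause in Section 9.3.2 that defers to the treating physician, with later confirmation by a panel or the study chair, concerns progression in non-target lesions only.
- The biopsy recommendation in the second note after the Section 9.3.3 table concerns residual lesions when CR is being called.

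Nothing requires a new lesion to be attributed to the study cancer.

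**2. The plan's own design figure.** Section 11.2 gives 10% versus 30%, alpha and beta 0.1, at least 2 of 16 to continue and at least 5 of 25 to succeed. With X1 ~ Bin(16, p) and X2 ~ Bin(9, p), the success probability is

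P(success) = sum over x = 2 to 16 of P(X1 = x) × P(X2 ≥ 5 − x).

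This is 0.0951 at p = 0.10 and 0.9030 at p = 0.30, so the stated rule meets its stated error rates.

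**3. Assumptions.** The documents give no rate of new primaries. I take λ = 0.1, 0.3 and 0.6 per patient-year, constant and independent of the index tumour, and a true 12-month PFS of 40%. None of these values comes from the documents.

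**4. PFS at 12 months.** Observed PFS = 0.40 × exp(−λ).

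| λ | exp(−λ) | Observed PFS | Points lost |
|---|---|---|---|
| 0.1 | 0.905 | 36.2% | 3.8 |
| 0.3 | 0.741 | 29.6% | 10.4 |
| 0.6 | 0.549 | 22.0% | 18.0 |

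**5. Response rate and power.** A response first seen at week 9 is confirmed 4 weeks later, at about week 13 (91 days, t = 91/365.25 = 0.249 years). The probability of a new primary by then is q = 1 − exp(−λt), and the observed rate is the true rate × (1 − q), put into the formula of step 2. The expected number of responders lost is 25 × 0.30 × q.

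| λ | q | True 30% reads | Power | Responders lost | True 10%: type I error |
|---|---|---|---|---|---|
| 0 | 0 | 30.0% | 0.903 | 0 | 0.095 |
| 0.1 | 2.5% | 29.3% | 0.889 | 0.18 | 0.088 |
| 0.3 | 7.2% | 27.8% | 0.858 | 0.54 | 0.074 |
| 0.6 | 13.9% | 25.8% | 0.804 | 1.04 | 0.057 |

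If exposure is counted only to the week-9 assessment named in Section 11.1.1, the rates are 29.5%, 28.5% and 27.0%, with power 0.894, 0.873 and 0.838. Week 13 is the better match to the confirmation rule. A response first seen at a later scan would be exposed for longer.

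**The case against.** **The text is silent rather than wrong.** Section 9.1 adopts RECIST v1.1 and speaks of tumour lesions, and Section 9.3.3 speaks of progression or recurrence of disease. An investigator might therefore take a new lesion to mean one of the study disease. That reading is possible, but the rule and the table are unqualified and nothing tells an investigator to apply it. If some did and others did not, the endpoint would differ between patients; with a cut-off of 5 responders in 25, a single call could decide the result.

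**The size is unknown.** This stands. Section 2.1 describes rising incidence of CSCC, not second primaries in patients with advanced disease. The eligibility limits on transplant patients and prednisone narrow the risk. Independence is also open to doubt: Section 2.1 lists topical 5-FU as a treatment for local CSCC, and Section 2.3 (Rationale) describes both drug classes as active in this disease, so new primaries on treatment could be fewer than assumed.

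**The effect is modest.** For response this stands at the two lower rates, where less than one responder is lost on average. For PFS, the sampling half-width at 40% with 25 patients and no censoring is 1.96 × √(0.4 × 0.6/25) = 19 points, larger than the 4 to 18 points above. PFS is also a descriptive endpoint. But imprecision does not remove a one-directional bias that is cheap to avoid.

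**Stronger readings a reader might infer.**

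- That 9.5%, 26% or 45% of patients would be called PD for this reason alone by 12 months. Those are 1 − exp(−λ) and ignore patients who progress or die first; the misclassified share at 12 months is 3.8, 10.4 or 18.0 points.
- That CLL patients are especially affected. They are eligible ("Patients with CLL or other hematologic malignancies are allowed as long as they meet other criteria listed above"), but no section links CLL to new skin cancers.
- That confirmed responses would be overturned, or that the trial could wrongly succeed. Neither follows: a confirmed response stands under Section 9.3.3, and type I error falls.

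**Conclusion.** The point holds as a defect in a stated rule. Followed as written, Sections 9.3.1-9.3.3 turn an unrelated new primary skin cancer into a PFS event, and into a lost response if it appears before confirmation. The direction is known: against the regimen, for both response and PFS.

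The size is not known. Under the assumed rates and independence, and an assumed true 12-month PFS of 40%, the PFS loss is 3.8 to 18.0 points. For a true response rate of 30%, the loss is 0.7 to 4.2 points and power falls to between 0.889 and 0.804. PFS is the main reason to act; the effect on the primary endpoint is small unless new primaries are frequent. The change should be made, but nothing here invalidates the two-stage design.

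**What to change.** Add to Sections 9.3.1-9.3.3: a new cutaneous lesion that routine pathology shows to be a new primary skin cancer, and not metastasis or recurrence of the index tumour, is recorded separately and does not count as a new lesion for response, duration of response or PFS. A new lesion without such pathology still counts. Add to Section 11.4 one PFS sensitivity analysis in which these new primaries are events.

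The cost is a few sentences, one recorded item and one extra table; no biopsy beyond routine care is needed. The downside is that separating a new primary from local spread takes some judgement. The conservative default and the sensitivity analysis bound its effect.

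Progression is also a reason for removal from the study (Section 3.5) and for ending treatment (Section 4.4). The sponsor should reconcile those sections with the new wording; no clinical rule is proposed here.
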